9.0 Data and Specimen Long Term Storage and Use

9.1 *If you will store data or specimens for future use, describe where you will store the data or specimens, how long they will be stored, and how and by whom the data or specimens will be accessed:*

Data will be coded using a 6 character number. Participant IDs will be created sequentially starting at YAEH01 . The key linking the participant name or identifiable information and the code will be stored on an encrypted server managed by the FBRI and HNFE IT department. This server can only be accessed by those on the research team. All study data will be kept on a separate server from identifiable information, also encrypted. Any paper documents generated that contain other identifiers, such as name, phone number, or email will be stored in a locked file cabinet accessible only by authorized staff. De-identified participant information will be kept indefinitely or at the written request of the participant. De-identified data and urine samples may be shared with others outside of the research team without reconsent.

Dietary recall data will be recorded using a standardized 24-hour recall form. Forms will be stored in a locked cabinet in Wallace Hall. Data will be analyzed using NDS-R on the password-protected desktop computer located in the PI [name]'s locked laboratory in Wallace Hall (rm 334).

Per Virginia Tech policy, in order to compensate participants, social security number (or Taxpayer ID) and street address will be collected via a W-9 form or W-8BEN. The participant address and SSN will be entered into the ClinCard systems, which is a HIPAA compliant payment system approved by Virginia Tech. After entry, this form will be given to and stored by the central administration at the FBRI to be used if it is required that a tax statement be sent to the participant, based on Federal Income Tax regulations. Study staff will not store any documents with SSN or address used for payment purposes.

9.2 *For specimens, list the data to be stored or associated with each specimen:*

N/A

9.3 *Describe the procedures to release data or specimens outside of the research team, including the process to request a release, approvals required for release, who can obtain data or specimens, and what data will be provided with specimens:*

N/A

9.4 *Describe the identifiers to be included with stored data or specimens, as well as any key or code that could be used to make them identifiable. Describe where the code will be stored, who will have access to it, and when it will be destroyed:*

Data will be coded using a 6 character number. Participant IDs will be created sequentially starting at YAEH01. The key linking the participant name or identifiable information and the code will be stored on an encrypted server managed by the FBRI and HNFE IT department. This server can only be accessed by those on the research team. All study data will be kept on a separate server from identifiable information, also encrypted. Any paper documents generated that contain other identifiers, such as name, phone number, or email will be stored in a locked file cabinet accessible only by authorized staff. De-identified/Identifiable participant information will be kept indefinitely destroyed 5 years after publication or at the written request of the participant. De-identified data and urine samples may be shared with others outside of the research team without reconsent.

Per Virginia Tech policy, in order to compensate participants, social security number (or Taxpayer ID) and street address will be collected via a W-9 form or W-8BEN. The participant address and SSN will be entered into the ClinCard systems, which is a HIPAA compliant payment system approved by Virginia Tech. After entry, this form will be given to and stored by the central administration at the FBRI to be used if it is required that a tax statement be sent to the participant, based on Federal Income Tax regulations. Study staff will not store any documents with SSN or address used for payment purposes.

9.5 *Please select the identifiers you will obtain (whether directly from participants or from another source), including but not limited to:*

	Name
	Geographical subdivisions smaller than a state, including street address, city, county, precinct, zip code, and equivalent geocodes (note, the initial three digits of a zip code are not considered identifiable)
	Elements of dates (except year) for dates directly related to an individual, including birth date, admission date, discharge date, date of death, and single year of age over 89 and all elements of dates (including year)

	indicative of such age (note, such ages and elements may be aggregated into a single category of age 90+)
	Phone numbers
	Fax numbers
	Electronic mail addresses (e-mail)
	Social Security numbers
	Medical record numbers
	Health plan beneficiary numbers
	Account numbers
	Certificate/license numbers
	Vehicle identifiers and serial numbers, including license plate numbers
	Device identifiers and serial numbers
	Web Universal Resource Locators (URLs)
	Internet protocol (IP) address numbers
	Biometric identifiers, including finger and voice prints (audio recording)
	Full face photographic images and any comparable images (including video recording)
	Student record number or identification number
	User name for online or computer accounts
	Any other unique identifying number, characteristic, or code (note this does not mean the unique code assigned by the investigator to code the data): Click here to explain.

10.0 Sharing of Results with Subjects

10.1 *Describe whether you will share results (study results or individual subject results, such as results of investigational diagnostic tests, genetic tests, or incidental findings) with subjects or others (e.g., the subject's primary care physician). If so, describe how you will share the results and include this information as part of the consent document. Upload materials you will use to explain the results to subjects:*

Participants will receive information about:

- dietary intake analysis
- height, weight, body composition
- copy of brain and abdomen MRI if desired

11.0 Study Timelines

11.1 *Describe:*

- *The duration of an individual subject's participation in the study (for example, 1 hour, 2-4 weeks, 3-5 years).*

- *The amount of time expected to enroll all study subjects (weeks, months, years, etc.)*
- *The amount of time expected for the investigators to complete this study including primary data analyses.*

The total estimated duration for individual participants is ~10-12 weeks involving 1-2 weeks of screening and baseline testing followed by 2, 14-day feeding periods; followed by 2 days of post-intervention testing and a 4 week washout period in between feeding conditions. The number of study visits will be ~34 and the total number of hours required for participation will be ~33-35 hours.

Approximately 1 year will be required to recruit and enroll participants. Approximately 1.5 - 2 years will be required to complete the study data collection and analysis. If recruitment goals are not met within 2 years, a 1-year no-cost extension will be requested from the NIH if study funds are available to continue recruitment and complete data collection/analysis.

12.0 Inclusion and Exclusion Criteria

12.1 Describe how you will screen individuals for eligibility. When will screening occur and what procedures will you use? Upload any screening scripts or surveys to Protocol Management:

Inclusion Criteria:

Age 18-25 years

Weight stable (+5 lbs) for previous 6 months

No plans to gain/lose weight or change physical activity level

Willing to pick up food daily and consume foods provided for two 14-day periods

Verbal and written informed consent

Unrestrained eater (TFEQ cognitive restraint score <11)

No reported history of eating disorders

Usual UPF intake +/-10% of US adolescent average of 68% total energy

Sedentary to recreationally active

*Individuals on a stable dose of thyroid medication (>6 mo) are eligible to participate, provided that they have been weight stable for the previous 6 months. Thyroid medication changes can cause weight instability.

Exclusion criteria:

BMI >30 kg/m²

Endocrine disorders* or other major chronic disease (e.g., type 2 diabetes, hypothyroidism, hypertension)

Pregnant or plans to become pregnant

Food allergies or aversions

Claustrophobia

History of head injury with loss of consciousness for more than 10 minutes

Contraindications to MRI: individuals with pacemaker, aneurysm clips, neurostimulators, cochlear implants, metal in eyes, steel worker, or other implants.

Eligibility Screening Procedures: Participants will first complete an online or phone pre-screening survey. If they are potentially eligible after completing the screening survey, they will be sent the informed consent document via email at least 24 hours prior to their initial screening and they will have an initial in-person screening visit scheduled.

Screening visit 1 (229 Wallace Hall): During the first in-person screening visit, a researcher will go over the informed consent document with the participant prior to collection of any data. If the participant gives consent, then the first screening visit will continue. Baseline screening measures will include: Health history form, screening forms for eating behavior (mYFAS, TFEQ), life events checklist (LEC5), habitual dietary intake (in person 24-hour recall), physical activity assessment questionnaire, height, and weight. Review protocol with the participant for two 24 hour recalls which will be done by phone.

Screening visit 2 ([name]-CHBR Suite): The second laboratory screening visit will consist of a mock fMRI scan to improve data quality and ensure participants are eligible and willing to complete the fMRI measurement. Participants will fill our clincard forms and receive clincard.

12.2 Describe the eligibility criteria that define who will be included and who will be excluded from enrollment for each procedure of your study.

Include any geographic criteria (e.g., Virginia Tech undergraduate students, a national sample of adults with engineering degrees, minors aged 8-12 in the New River Valley, university faculty in Virginia and Paris, France):

Inclusion Criteria:

Age 18-25 years

Weight stable (+5 lbs) for previous 6 months

No plans to gain/lose weight or change physical activity level

Willing to pick up food daily and consume foods provided for two 14-day periods

Verbal and written informed consent

Unrestrained eater (TFEQ cognitive restraint score <11)

No reported history of eating disorders and EAT-26 score <20

Usual UPF intake +/-10% of US adolescent average of 68% total energy

Sedentary to recreationally active

*Individuals on a stable dose of thyroid medication (>6 mo) are eligible to participate.

Exclusion criteria:

BMI >30 kg/m²

Endocrine disorders* or other major chronic disease (e.g., type 2 diabetes, hypothyroidism, hypertension)

Pregnant or plans to become pregnant

Food allergies or aversions

Claustrophobia

History of head injury with loss of consciousness for more than 10 minutes

Contraindications to MRI: individuals with pacemaker, aneurysm clips, neurostimulators, cochlear implants, metal in eyes, steel worker, or other implants.

No geographical criteria as long as participants are willing to pick up study food daily on the Virginia Tech Blacksburg campus and complete baseline and post study measurements at the Roanoke Campus.

12.3 Indicate specifically whether you will include or exclude each of the following special populations: (You may not include members of these populations as subjects in your research unless you indicate them in the description of your subject population.)

- *Minors, as defined by state law where the study is performed (infants, children, teenagers)*
- *Pregnant women (can be included in minimal risk studies by mentioning in section 13.1)*
- *Prisoners (including all incarcerated individuals)*
- *Adults not capable to consent on their own behalf*

No vulnerable populations listed above will be included.

13.0 Vulnerable Populations

13.1 If the research involves individuals who are vulnerable to coercion or undue influence, please describe additional safeguards you will include to protect their rights and welfare. Consider the applicable items listed below:

- *If the research involves Virginia Tech students, indicate whether these are students of any of the investigators. If so, describe whether the activities will take place during class time as part of the curriculum and the steps you will take to reduce the possibility that students feel obliged to participate in order to improve their course grade. The HRPP can provide further guidance as needed. Describe whether you will request access to student records (e.g., SAT, GPA, GRE scores).*
- *If the research involves employees of Virginia Tech or the research sponsor, describe steps you will take to ensure that the employees*

are freely participating and describe how their data will be protected from inspection by their supervisors.

- *If the research involves Virginia Tech NCAA athletes, you must obtain approval from the athletic department.*
- *For research involving Montgomery County Public Schools, you must obtain county approval (after obtaining contingent Virginia Tech approval). Other locales have different requirements; please check on these and describe here. Approval is typically granted by the superintendent, principal, and classroom teacher (in that order). Approval by an individual teacher is insufficient. School approval, in the form of a letter or a memorandum should be uploaded as a supporting document.*
- *If the research involves pregnant women, review “CHECKLIST: Pregnant Women (HRP-412)” to ensure that you have provided sufficient information in this protocol.*
- *If the research involves prisoners, review “CHECKLIST: Prisoners (HRP-415)” to ensure that you have provided sufficient information in this protocol.*
- *If the research involves persons who have not attained the legal age for consent to treatments or procedures involved in the research (minors), review the “CHECKLIST: Minors (HRP-416)” to ensure that you have provided sufficient information in this protocol.*
- *If the research involves cognitively impaired adults, review “CHECKLIST: Cognitively Impaired Adults (HRP-417)” to ensure that you have provided sufficient information in this protocol.*

N/A

14.0 Number of Subjects

14.1 *Indicate the total number of subjects to be enrolled and how this number was determined (e.g., sample size calculation [show], number of available subjects in a finite pool, number of tests funding award would allow):*

Planned enrollment is 32 participants.

Briefly, for the primary aim, a power analysis based on effect sizes from the literature was conducted using the pwr toolbox in R, from which a sample size of 26 was determined. For the secondary aim, effect size was calculated using effsize and a power analysis was conducted using pwr, which determined 13 participants were needed. Therefore, we will recruit 33 participants to account for 20% attrition, for a final sample of 26.

14.2 If this is a multi-site study, indicate the number of subjects to be enrolled at this site and the total to be enrolled from all sites:

N/A

14.3 If applicable, indicate the number of potential subjects you expect to screen for enrollment, and the number of subjects you will need to complete the research procedures:

Based upon previous experience implementing studies with similar protocols, we expect to screen 100-150 subjects, for a final enrollment of 32.

14.4 If the study has more than one procedure, indicate the total number of subjects to undergo each procedure separately:

N/A

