1.0 Study Summary

Study Title	Influence of ultra-processed foods on reward processing and energy intake
Study Design	The study will utilize a randomized crossover design, with 2 weeks of controlled feeding followed by measuring changes in reward processing by fMRI. The overall objective of this study is to establish proof-of-concept for an altered reward processing in response to a UPF diet compared to a diet emphasizing MPF in the key developmental period of 18-25.
Primary Objective	To determine the influence of chronic UPF consumption on brain reward response to UPF.
Secondary Objective(s)	To determine the influence of chronic UPF consumption on ad libitum energy intake and food selection. Explore the influence of UPF consumption on executive function, specifically inhibitory control, cognitive flexibility, and working memory, as well as eating in the absence of hunger.
Study Population	Late adolescents/early adults aged 18-25
Sample Size	32
Research Intervention(s)/Investigational Agent(s)	Participants will be randomly assigned to a 2-week diet emphasizing either UPF (81% total energy) or un/minimally processed foods (0% UPF). Participants will be fed a eucaloric diet (50% carbohydrate, 35% fat, 15% protein) matched for dietary fiber, added sugars, saturated fat, mono- and poly-unsaturated fat, sodium, pre- and probiotics, micronutrients, and overall diet quality, for the duration of the study to avoid potential confounds of weight change and other dietary factors which may influence study outcomes. fMRI will be conducted 4 times where participants will be exposed to UPF milkshakes to assess reward processing. Ad libitum energy intake will be assessed.
Study Duration for Individual Participants	1-2 weeks of screening and baseline testing followed by 2, 14-day feeding periods; followed by 2 days of post-intervention testing and a 4 week washout period in between feeding conditions. The total estimated duration for participants is ~10-12 weeks.
Acronyms and Definitions	UPF: Ultra-processed food MPF: Minimally processed food EI: Energy intake EF: Executive function ED: Eating disorders PA: Physical activity LHS: Labeled Hedonic Scale HEI: Healthy Eating Index TFEQ: Three-Factor Eating Questionnaire mYFAS: modified Yale Food Addiction Scale

	LEC5-Life Events Checklist 5 BIA: Bioelectrical Impedance Analysis DD: Delay Discounting
--	--

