5.0 Study Design and Statistical Analysis Plan

5.1 *Describe the basic study design/approach (e.g., qualitative study using five focus groups of first year students to describe assimilation into the university community; randomized controlled trial of a behavioral change intervention to increase dietary intake of whole grains; pre- post-test evaluation of new pedagogical techniques to improve adult literacy):*

Individuals aged 18-25 years (n=32), will undergo two 14-day controlled feeding conditions in a randomly assigned order (crossover): un/minimally processed diet (0% UPF, “MPF”) or a diet containing 81% energy from UPF (“UPF”). Randomization sequence will be stratified based upon BMI status, sex, and age (18-21y, 22-25y). Diets will be eucaloric and matched for potential confounding factors including macronutrients, fiber, and energy density. A 4-week washout period will occur between dietary conditions. To assess changes in reward processing, brain response to a UPF-rich beverage (“milkshake”) will be assessed via fMRI before and after each feeding period. Executive function will also be assessed before and after each feeding period. Measurements immediately following each feeding period will include ad libitum EI and

food selection containing both UPF and MPF and eating in the absence of hunger post-meal.

5.2 Describe corresponding data analysis plan/approach (e.g., content analysis of focus group transcripts; descriptive analysis followed by linear regression modeling; nonparametric analysis of pre- and post-test measures):

Effects on study outcomes will be assessed using mixed effect linear models to estimate treatment differences between diet conditions. Exploratory path analysis with multiple mediators will be utilized to understand mechanisms of change, and estimate effect sizes. Covariates will be included to control for baseline group differences, if any. Standard preprocessing and statistical techniques for fMRI data to look for relationships between neural activity and physiological measures upon chronic exposure to UPF. Standard fMRI processing techniques will also be used to calculate subcutaneous, visceral, and liver fat percentages.

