26.0 Resources Available

26.1 Describe the resources available to conduct the research. For example, as appropriate:

- *Describe the PI’s availability to supervise the research.*
- *Justify the feasibility of recruiting the required number of suitable subjects within the agreed recruitment period. For example, how many potential subjects do you have access to? What percentage of those potential subjects do you need to recruit?*
- *Describe the time that you will devote to conducting and completing the research.*
- *Describe your facilities.*
- *Describe the availability of medical or psychological resources that subjects might need as a result of an anticipated or unanticipated consequence of participation in the research.*
- *Describe your process to ensure that all persons assisting with the research are adequately informed about the protocol, the research procedures, and their duties and functions (e.g., training plans, detailed study notebooks).*

This research project is supported through a 2-year grant from the National Institute of Aging at the NIH. The PIs, [name] and [name], have devoted 10% effort to this grant/research study. All co-investigators are supported at 5% effort for this research, for

two years. Graduate student support is also available for this trial. All graduate students, undergraduate students, Co-I's and study staff will be trained in all procedures and complete protection of human research participant training. Study staff will be trained in all procedures prior to study onset, and a Manual of Procedures will be available for staff training and reference.

Our research group has successfully completed numerous large-scale NIH-funded intervention trials in this region, including those using controlled feeding procedures. The MPI have experience with recruiting and retaining uniquely challenging study populations, such as young adults, and young children and adolescents (n=337 recruited in 1.5 years, 49% male, 90% retention; R21 HD078636). Given our experiences, enrolling 32 individuals in 1-1.5 years is feasible. If recruitment targets are not met and support is available, recruitment will continue and a no-cost extension requested from the NIH.

Facilities:

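### Section 14.1 gives two enrolment numbers, 32 and 33, and the 32 used everywhere else falls just short of the stated 20% attrition allowance

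*Combined protocol and SAP*

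**What the plan says.** The first sentence of the answer in section 14.1 reads "Planned enrollment is 32 participants". The next paragraph reports that the power analysis for the primary aim gave 26 and the one for the secondary aim gave 13, and concludes: "Therefore, we will recruit 33 participants to account for 20% attrition, for a final sample of 26".

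Everywhere else the number is 32:

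- Section 1.0, summary table: "Sample Size 32".
- Section 5.1: "Individuals aged 18-25 years (n=32), will undergo two 14-day controlled feeding conditions". Section 8.1 repeats this sentence.
- Section 14.3, after an expected 100 to 150 screened: "for a final enrollment of 32".
- Section 26.1: "enrolling 32 individuals in 1-1.5 years is feasible".

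Section 14.1 gives neither an inflation formula nor a rounding rule. The revision history records no change to the sample size, so both numbers are current text.

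**The concern.** Item 14.1 of the form asks for the total to be enrolled and for how it was determined. The only derivation offered ends at 33. The number the trial will work to, 32, has no stated derivation and does not follow from the 20% allowance under the usual calculation.

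No wording in the document makes 33 a different quantity, such as people recruited before a later loss on the way to randomisation. The 20% is applied to 33 to arrive at 26 completers, which is the role of an enrolment number. The screening count is given separately in section 14.3.

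The enrolment and completer numbers are the benchmarks against which the trial's conduct will be judged. With both numbers standing, a trial that enrols 32 could be reported as having met its target or as having missed it by one. The final sample of 26 is also exactly what the primary aim requires, so the attrition allowance is the only margin the plan states.

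**Working it through.** **Inputs, all from section 14.1 unless noted**

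- Completers needed for the primary aim: n = 26. The secondary aim needs 13, so the primary aim governs.
- Attrition allowance: d = 20%.
- Enrolment: 32 (first sentence; also sections 1.0, 5.1, 8.1, 14.3 and 26.1) or 33 (last sentence of the sample-size paragraph).

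**Step 1. Reproduce the plan's 33.** The usual inflation is N = n/(1 − d), rounded up: 26/(1 − 0.20) = 32.5, which gives 33. The stated figure reproduces exactly.

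**Step 2. Look for a route to 32.** Multiplying instead of dividing gives 26 × 1.20 = 31.2, rounded up to 32. Rounding 32.5 down also gives 32. The document mentions neither, so the origin of 32 is unknown.

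**Step 3. Test each number against the stated allowance.**

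| | 32 enrolled | 33 enrolled |
|---|---|---|
| Expected completers at 20% attrition | 32 × 0.80 = 25.6 | 33 × 0.80 = 26.4 |
| Expected losses at 20% | 32 × 0.20 = 6.4 | 33 × 0.20 = 6.6 |
| Losses allowed if 26 are to remain | 32 − 26 = 6 | 33 − 26 = 7 |
| Attrition allowed | 6/32 = 18.75% | 7/33 = 21.2% |

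The expected losses exceed the allowed losses for 32 (6.4 against 6) and stay within them for 33 (6.6 against 7).

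**Step 4. Chance of keeping at least 26.** Assume that each participant drops out independently with probability 0.20. The number of completers is then binomial, and the probability of 26 or more is 53.5% with 32 enrolled and 66.6% with 33. Neither number makes 26 certain; the extra participant adds about 13 percentage points.

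**Step 5. What one completer is worth.** The plan gives no effect size, significance level, sidedness or power for the 26, so this is an illustration only. Assume a two-sided paired t-test at 0.05. If 26 was chosen for 80% power, 25 completers give about 78.3%. If it was chosen for 90%, 25 give about 88.7%. The loss is between 1 and 2 percentage points.

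**The case against.** The strongest reply is that this is rounding. The exact requirement is 32.5, the two numbers lie on either side of it, and 20% is itself a round planning figure. Three further points support that reply.

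- The only retention figure in the document, 90% in an earlier study by the same group (section 26.1), would leave 32 × 0.90 = 28.8 expected completers, comfortably above 26.
- The mixed models in section 5.2 can use data from a participant who finishes only one period, so a drop-out need not be a total loss. Section 16.3 limits this, since it rules out partial withdrawal and deals with participants who want their information destroyed.
- The plan has ways to react. The monitoring tables in sections 17.2 and 21.1 schedule a semi-annual report on what drop-outs mean for power. Section 11.1 says "If recruitment goals are not met within 2 years, a 1-year no-cost extension will be requested from the NIH", provided funds remain, and section 26.1 adds "If recruitment targets are not met and support is available, recruitment will continue".

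All of this stands as to weight: the practical risk is small, and the sentence ending in 33 contains no arithmetic error in itself. None of it says which number is the target. The drop-out report and the recruitment extension both need a target to measure against. Retention in a different study may suggest that 20% is cautious, but it does not change the allowance this plan states.

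**Conclusion.** The point holds, at low severity. Section 14.1 contains two unreconciled enrolment numbers, and the one used in the rest of the document does not deliver 26 expected completers at 20% attrition. The shortfall is 26 − 25.6 = 0.4 of an expected completer, or one permitted loss fewer than with 33. This rests on the usual inflation N = n/(1 − d), which reproduces the plan's own 33, and on reading the 20% as attrition among those enrolled. The size of the effect on power cannot be derived from the document. Under the paired-test assumption above it is negligible for the trial's conclusions. Because the sample size is a figure that others will rely on, it should be corrected and not left to interpretation.

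**What to change.** State one enrolment number throughout, with its own attrition allowance.

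**Keep 32.** Replace the last sentence of the sample-size paragraph in section 14.1 with: *32 participants will be enrolled, which allows up to 6 losses (about 19% attrition) for a final sample of 26.* This costs one sentence and no extra participant. It does lower the stated allowance from 20% to 18.75%, which the sponsor should accept knowingly.

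**Or adopt 33.** If the 20% allowance is to stand, write 33 in sections 1.0, 5.1, 8.1, 14.1 (first sentence), 14.3 and 26.1, and on any page outside the reviewed text that repeats the number. This costs one more participant and six edits.

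The choice is the sponsor's. Either option resolves the inconsistency.
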